5.4.2 Nivolumab and Ipilimumab Dose Levels

Missed doses of nivolumab and ipilimumab drugs should not be made up if not administered within the window specified by the protocol. Administration of nivolumab and ipilimumab should remain synchronized for patients on both drugs. No dose levels or schedule changes exist for nivolumab and ipilimumab – the drugs are either administered (together for the combination arm) or held at each given time. If held they may be given at the next specified interval in the protocol.

If all treatment is held for more than 56 days (8 weeks), the patient must be permanently discontinued from study therapy unless study chair approval is obtained for unusual circumstances.

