\geq 50% increase of AST or ALT and at least one of AST or ALT is Grade 3 (i.e. AST or ALT $>$ 5.0 but \leq 20.0 x ULN)	Hold all study treatment and monitor with twice weekly LFTs until Grade \leq 2. Then continue with at least weekly LFTs until resolution to Grade \leq 1. Study treatment may then be resumed at a one-dose-level reduction of cabozantinib.

Grade 4	Discontinue all study treatment permanently. LFTs should be monitored as clinically indicated, i.e. 2 times per week or more, until resolution to Grade ≤ 1. If the subject was unequivocally deriving clinical benefit, the subject may be able to resume treatment with cabozantinib at a lower dose as determined by the investigator and Study Chair but only with Study Chair approval.
Bilirubin elevation Grade	
Grade 2 Bilirubin	Continue study treatment. Consider more frequent monitoring of bilirubin, i.e. weekly or more
Grade 2 or greater Bilirubin (and > 2.0 ULN), with Grade 3 or greater transaminase elevation, without evidence of biliary obstruction (i.e. elevation of alkaline phosphatase) or alternative explanation	Permanently discontinue all study treatment due to likely signal of severe liver injury
Grade 3 Bilirubin (> 3.0 ULN), isolated	Hold all study treatment until recovered to Grade ≤ 1 or baseline, INR < 1.5 ULN or baseline, and aminotransferases Grade ≤ 1 or baseline. Cabozantinib may then be resumed at a one-dose-level reduction.
Grade 4 Bilirubin (> 10.0 ULN)	Permanently discontinue cabozantinib

Cabozantinib associated asymptomatic Lipase or Amylase Elevations

NOTES: Amylase and lipase elevations have been observed in clinical studies with cabozantinib. The clinical significance of asymptomatic elevations of enzymes is not known but in general have not been associated with clinically apparent sequelae. It is recommended that subjects with lipase elevation and/or symptoms of pancreatitis have more frequent laboratory monitoring of lipase and/or amylase (2-3 times per week). Subjects with symptomatic pancreatitis should be treated with standard supportive measures.

Asymptomatic Lipase or Amylase Elevations

Grade 1 or Grade 2	Continue at current dose level. More frequent monitoring is recommended

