Grade 3	Hold all study treatment Monitor lipase and amylase twice weekly Upon resolution to Grade ≤ 1 or baseline, study treatment may be restarted at the same dose or at a reduced dose provided that this occurs within 4 weeks. If retreatment following Grade 3 lipase or amylase elevation is at the same cabozantinib dose and Grade 3 or Grade 4 elevations recur, then all study treatment must be held again until lipase and amylase levels have resolved to Grade ≤ 1 or baseline and retreatment must be at a reduced dose.
Grade 4	Hold all study treatment Monitor lipase and amylase twice weekly Upon resolution to Grade ≤ 1 or baseline and if resolution occurred within 4 days, cabozantinib may be restarted at the same dose or a reduced dose. If resolution took more than 4 days, the dose must be reduced upon retreatment provided that resolution occurred within 4 weeks. If retreatment following Grade 4 lipase or amylase elevation is at the same cabozantinib dose and Grade 3 or 4 elevations recur, then all study treatment must be held again until lipase and amylase have resolved to Grade ≤ 1 or

	baseline and retreatment must be at a reduced dose.
--	-----------------------------------------------------

Cabozantinib-associated Pancreatitis

Pancreatitis	
Grade 3	Hold cabozantinib treatment. Radiographic evaluation is recommended. Monitor lipase and amylase weekly. Upon resolution to Grade ≤ 1 or baseline, cabozantinib may be restarted at a reduced dose.
Grade 4	Permanently discontinue all study treatment. However, if the subject was unequivocally deriving benefit from therapy, cabozantinib treatment may resume at a reduced dose agreed to by the investigator and Study Chair but only with Study Chair approval.

[figure not shown]
Immune-related hepatobiliary disorders

Liver Function AST, ALT, Bilirubin	Management/Next Dose for Nivolumab+-Ipilimumab
≤ Grade 1	Hold until UNL or baseline. Resume at same dose level.
Grade 2	Hold until UNL or baseline. Resume at same dose level.
Grade 3	Off protocol therapy
Grade 4	Off protocol therapy
Continued treatment of active immune mediated hepatitis may exacerbate ongoing inflammation. Holding drug to evaluate LFT changes and early treatment are recommended.	
LFT changes may occur during steroid tapers from other events and may occur together with other GI events including cholecystitis/pancreatitis.	
Recommended management: see Hepatic AE management algorithm	

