Pancreatitis Amylase/Lipase	Management/Next Dose for Nivolumab+-Ipilimumab
≤ Grade 1	May continue at same dose level if asymptomatic; consider liver ultrasound and/or abdominal CT scan if no resolution.
Grade 2	May continue at same dose level if asymptomatic; consider liver ultrasound and/or abdominal CT scan if no resolution.
Grade 3	May continue at same dose level if asymptomatic; consider liver ultrasound and/or abdominal CT scan if no resolution.
Grade 4	Hold drug. Perform liver ultrasound and/or abdominal CT scan to rule out radiographic pancreatitis. Resume at same dose level if asymptomatic and no radiographic clinical concerns. Patients who develop symptomatic pancreatitis or DM should be taken off treatment
Patients may develop symptomatic and radiologic evidence of pancreatitis as well as DM and DKA. Lipase elevation may occur during the period of steroid withdrawal and with other immune mediated events or associated with colitis, hepatitis, and patients who have asymptomatic lipase elevation typically have self-limited course and may be retreated.	
For treatment management of symptomatic pancreatitis please follow the Hepatic Adverse Event Management Algorithm	

Hepatic Adverse Event Management Algorithm

Rule out non-inflammatory causes. If non-inflammatory cause, treat accordingly and continue I-O therapy. Consider imaging for obstruction.

Patients on IV steroids may be switched to an equivalent dose of oral corticosteroids (e.g. prednisone) at start of tapering or earlier, once sustained clinical improvement is observed. Lower bioavailability of oral corticosteroids should be taken into account when switching to the equivalent dose of oral corticosteroids.

*I-O therapy may be delayed rather than discontinued if AST/ALT ≤ 8 x ULN and T.bili ≤ 5 x ULN.

**The recommended starting dose for grade 4 hepatitis is 2 mg/kg/day methylprednisolone IV.

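### Section 5.4.9 gives conflicting instructions for nivolumab with or without ipilimumab: stop or delay for part of the grade 3 liver range (all arms), and hold or continue for asymptomatic grade 3 lipase or amylase (Arms B, C and T)

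*Combined protocol and SAP*

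**What the plan says.** Section 5.4.9 holds two sets of guidance, one headed as cabozantinib-associated and one as immune-related.

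**Liver, immune-related.** The table for nivolumab with or without ipilimumab gives "Off protocol therapy" for grade 3 AST, ALT or bilirubin, with no exception, and closes with "Recommended management: see Hepatic AE management algorithm". A footnote to that algorithm reads "I-O therapy may be delayed rather than discontinued if AST/ALT ≤ 8 x ULN and T.bili ≤ 5 x ULN".

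**Liver, cabozantinib-associated.** For patients whose AST or ALT was raised at baseline and who reach grade 3, all study drugs are held, and then "Study treatment may then be resumed at a one-dose-level reduction of cabozantinib". If bilirubin exceeds 2 x ULN together with grade 3 or greater transaminases, and there is no obstruction or other explanation, all study drugs are stopped permanently.

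**Lipase or amylase, asymptomatic grade 3.** The cabozantinib table suspends all study drugs, and after recovery "study treatment may be restarted at the same dose or at a reduced dose provided that this occurs within 4 weeks". The immune-related table says of nivolumab with or without ipilimumab: "May continue at same dose level if asymptomatic; consider liver ultrasound and/or abdominal CT scan if no resolution".

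**Status of the guidance.** Section 5.4.3 states that the management guidelines are not obligatory and leave room for investigator judgement. Where they call for permanent discontinuation, the study chair may approve a restart. It also concedes that attribution can be hard on combination therapy.

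**The concern.** A site that follows 5.4.9 faithfully can reach different actions for the same liver value in the same patient. The table and the footnote concern the same drugs and the same presumed immune cause, so deciding on attribution does not settle the matter. It also changes the route back to treatment. Under the table, resuming immunotherapy is an exception needing study chair approval; under the footnote it is the end of an ordinary delay. At stake are re-exposure after possible immune hepatitis at one site, loss of therapy at another, and recorded reasons for stopping that partly reflect which text was read. The last bears on the toxicity description in objective 2.2.4.

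The lipase conflict matters less for any one patient, since it is a hold against continuation. It can arise only where cabozantinib is given, so it can affect immunotherapy exposure in Arms B, C and T but not in Arm A.

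**Working it through.** The plan states no figure on this point. The check sets the instructions side by side and intersects their limits.

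**Grade limits printed in 5.4.9.** Grade 3 AST/ALT: above 5.0 and up to 20.0 x ULN. Grade 3 bilirubin: above 3.0 x ULN, with grade 4 above 10.0. The AST/ALT range is printed in the row for patients with raised baseline values; I assume that it applies to all patients.

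**Liver: immune table against footnote (Arms A, B, C, T, all of which receive nivolumab).** The footnote requires both AST/ALT ≤ 8 and bilirubin ≤ 5 x ULN.

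| Value (x ULN) | Immune table | Footnote |
|---|---|---|
| AST/ALT > 5 to 8, bilirubin ≤ 5 | off therapy | delay permitted |
| Bilirubin > 3 to 5, AST/ALT ≤ 8 | off therapy | delay permitted |
| AST/ALT > 8 to 20, or bilirubin > 5 to 10 | off therapy | no relief, so no conflict |

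Example: AST 6 x ULN with normal bilirubin is off therapy by the table and may be a delay by the footnote.

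**Liver: added instructions in Arms B, C and T.** With a raised baseline, the same AST of 6 x ULN (if at least 50% above baseline) leads to a hold of all study drugs and later resumption. With AST 6 x ULN, bilirubin 2.5 x ULN and no obstruction or other explanation, the cabozantinib table stops all study drugs permanently, while the footnote still permits delay of immunotherapy.

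**Lipase or amylase: asymptomatic grade 3 (Arms B, C, T).** Cabozantinib table: hold all study drugs. Immune table: immunotherapy may continue. For grade 3 pancreatitis, by contrast, the cabozantinib table holds cabozantinib alone, so the scope of the hold also varies within the cabozantinib guidance.

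**Rough scale.** Counts are from the section 1.2 safety table; 43 is the number of eligible and treated patients per arm in section 9.4.

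- Grade 3 lipase, doublet: 2/30 = 6.7%; 43 x 2/30 = 2.9, about 3 patients.
- Grade 3 lipase, triplet: 2/18 = 11.1%; 43 x 2/18 = 4.8, about 5 patients. (The table prints 13% beside this count; I use the count.)
- Grade 3 ALT, doublet: 0/30. Triplet: 1/18 = 5.6%; 43 x 1/18 = 2.4, about 2 patients. Grade 3 AST: 0 in both groups.

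The lipase counts do not separate asymptomatic cases. The ALT count does not say whether the value lay at or below 8 x ULN. The source is a genitourinary phase I study with different immunotherapy schedules, and it offers nothing for Arm A.

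**The case against.** The strongest reply is that 5.4.3 makes these tables advisory and gives the study chair power to approve a restart. A reader might infer that discontinuation throughout the trial turns on which table a site opens; that goes too far, because judgement and the study chair stand between table and outcome. What remains is that discretion does not tell a site which instruction is the default.

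The second reply is attribution. It is tempting to say that an asymptomatic enzyme rise cannot be attributed at all. The documents do not support that: the likelihood table in 5.4.3 rates amylase/lipase increase as less common with cabozantinib and infrequent as an immune effect, and 5.4.4 offers holding cabozantinib and observing. This helps with lipase and with the added cabozantinib rows. It leaves the liver table and footnote untouched, since both are immune guidance. It also does not say what governs immunotherapy while the cause is unclear; 5.4.25 ties cabozantinib adjustment to even a possible relation, so both tables can apply to one value.

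Other stronger readings also fail:

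- That one laboratory value can lead to stopping, delay or uninterrupted dosing. This merges two analytes. Liver gives stop, delay or hold; lipase gives hold or continue.
- That the 4-week lipase limit contradicts section 5.4.2, "If all treatment is held for more than 56 days (8 weeks), the patient must be permanently discontinued from study therapy". The latter is an outer limit, and a shorter event-specific limit fits inside it.
- That grade 4 lipase belongs in the count. Both tables begin with a hold at grade 4.
- That PFS is distorted. Section 5.8 continues radiographic follow-up to progression after early discontinuation, even if other therapy starts, and the documents give no basis for an estimate.

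Finally, the algorithm diagram was not available to read, so the box that the footnote qualifies could not be seen. The footnote's limits still extend into grade 3, which the table ends without qualification.

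**Conclusion.** The point stands as two textual conflicts over immunotherapy in 5.4.9. The liver conflict applies in all arms but only in the lower part of grade 3, and its outcomes are discontinuation or delay; the cabozantinib rows add further differing actions in Arms B, C and T. The lipase/amylase conflict applies only in Arms B, C and T and is hold against continue. On the section 1.2 counts, the likely numbers are small: about 3 and 5 of 43 with grade 3 lipase on doublet and triplet, an upper figure for the conflicting row if some were symptomatic, and about 2 of 43 with grade 3 ALT on the triplet. These rest on 2, 2 and 1 observed patients in a different disease. No effect on PFS, events or power can be derived. The case for acting rests on patient safety and consistent conduct, because one of the conflicts is in a stopping instruction for possible immune hepatitis.

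**What to change.** Amend 5.4.9 so that one instruction applies to each value:

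1. Reconcile the grade 3 row of the immune liver table with the algorithm footnote over the overlapping ranges.
2. Reconcile the cabozantinib transaminase, bilirubin and lipase/amylase rows that act on all study drugs with the immune tables, and state which table governs nivolumab and ipilimumab in Arms B, C and T when attribution is unclear.
3. Check the footnote against the algorithm diagram, so that the box it qualifies agrees with the table.

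Which clinical rule applies is for the study chair and CTEP to decide. The cost is a wording amendment to one section, with no new assessments and no change to the sample size or analysis.

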5.4.10 Pneumonitis

[figure not shown]
Management of cabozantinib associated pneumonitis

Pneumonitis has been associated with cabozantinib, nivolumab, and ipilimumab therapies individually. In general it is difficult to definitively diagnose and can be life threatening. Patients with proven symptomatic clinically proven pneumonitis refractory to management guidelines for nivolumab +/- ipilimumab (below) should have cabozantinib permanently discontinued, if they were on cabozantinib therapy.

Pneumonitis	Management/Next Dose for Nivolumab+/-Ipilimumab
≤ Grade 1	Hold dose pending evaluation and resolution to baseline including baseline pO2. Resume no change in dose after pulmonary and/or ID consultation excludes lymphocytic pneumonitis.
Grade 2	Hold dose pending evaluation. Resume no change in dose after pulmonary and/or ID consultation excludes ipilimumab and associated lymphocytic pneumonitis as the cause of the pneumonitis. Off study if steroids are required. ^
Grade 3	Hold dose pending evaluation. Resume no change in dose after pulmonary and/or ID consultation excludes ipilimumab and associated lymphocytic pneumonitis as the cause of the pneumonitis. Off study if steroids are required
Grade 4	Off protocol therapy
Distinguishing inflammatory pneumonitis is often a diagnosis of exclusion for patients who do not respond to antibiotics and have no causal organism identified including influenza. Most patients with respiratory failure or hypoxia will be treated with steroids. Bronchoscopy may be required and analysis of lavage fluid for lymphocytic predominance may be helpful. Patients with new lung nodules should be evaluated for sarcoid like granuloma. Please consider recommending seasonal influenza killed vaccine for all patients.	
Recommended management: See Pulmonary Adverse Event Management Algorithm	

Pulmonary Adverse Event Management Algorithm

Rule out non-inflammatory causes. If non-inflammatory cause, treat accordingly and continue I-O therapy. Evaluate with imaging and pulmonary consultation.

Patients on IV steroids may be switched to an equivalent dose of oral corticosteroids (e.g. prednisone) at start of tapering or earlier, once sustained clinical improvement is observed. Lower bioavailability of oral corticosteroids should be taken into account when switching to the equivalent dose of oral corticosteroids.

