Toxicology

A maximum tolerated dose (MTD) of nivolumab was not defined (Topalian et al., 2012). Serious adverse events (SAEs) occurred in 32 of 296 patients (11%) similar to the immune-related inflammatory events seen with ipilimumab: pneumonitis, vitiligo, colitis, hepatitis, hypophysitis, and thyroiditis (with noted pulmonary toxicity resulting in 3 deaths). Renal failure, symptomatic pancreatic and DM, neurologic events, and vasculitis have also been reported.). In combination with ipilimumab in the concurrent-regimen group (Wolchok et al., 2013), grade 3 or 4 treatment-related events were noted in 53% of patients. Skin rash represents the majority of these events.

Pharmacodynamics/Biomarkers

Tumor-cell expression (melanoma) of PD-L1 was characterized in combination with ipilimumab with the use of IHC staining and pharmacodynamics changes in the peripheral-blood absolute lymphocyte count (Wolchok et al., 2013). With PD-L1 positivity defined as expression in at least 5% of tumor cells, biopsy specimens from 21 of 56 patients (38%) were PD-L1-positive. Among patients treated with the concurrent regimen of nivolumab and ipilimumab, ORs were observed in patients with either PD-L1-positive tumor samples (6 of 13 patients) or PD-L1-negative tumor samples (9 of 22). In the sequenced regimen cohorts, a higher number of overall responses was seen among patients with PD-L1-positive tumor samples (4 of 8 patients) than among patients with PD-L1-negative tumor samples (1 of 13) suggesting the possibility that these tumors have higher response rates to the combination. The relationship between PDL-1 expression and responses may not be present in patients treated with the combination. Tissue expression of PDL-2, interferon- γ (IFN- γ), IDO, and T cell CD8+ are of current interest. Until more reliable data based on standardized procedures for tissue collection and assays are available, PD-L1 status cannot be used to select patients for treatment at this time.

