5.1.3 ARM C

Nivolumab 480 mg IV over 60 minutes every 4 weeks, ongoing

Cabozantinib 40 mg PO daily, ongoing

Ipilimumab 1 mg/kg over 90 minutes every 8 weeks, ongoing

NOTE: On days when both nivolumab and ipilimumab are administered, nivolumab is administered prior to ipilimumab.

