5.4.19 Myocarditis

Management of cabozantinib related

cardiomyopathy/myocarditis: Cardiomyopathy has been reported with VEGF-pathway inhibitors, but myocarditis is very infrequent at most. Therefore, immune related causes should be primarily suspected but cabozantinib should also be held while workup is ongoing.

Management of immune related cardiomyopathy/myocarditis: Myocarditis, that may result in cardiomyopathy, has been increasingly reported as a complication of immunotherapy.

Guidelines for management are presented in the table below.

- Drug will be held for grade 2 cardiac dysfunction pending evaluation
- Drug will be permanently discontinued for grade 3 or 4 cardiac dysfunction and grade 2 events that do not recover to baseline or that reoccur
- Treatment with steroids as clinically indicated

Cardiac*	Management/Next Dose for BMS-936558 (Nivolumab) + Ipilimumab Cardiac Toxicities
≤ Grade 1	Hold dose pending evaluation and observation** Evaluate for signs and symptoms of CHF, ischemia, arrhythmia or myositis. Obtain history EKG, CK (for concomitant myositis), CK-MB, Troponin I. Repeat troponin, CK and EKG 2-3 days. If troponin and labs normalize may resume therapy. If labs worsen or symptoms develop then treat as below. Hold pending evaluation.
Grade ≥ 2 with suspected myocarditis	Hold dose** Admit to hospital. Cardiology consult. Rule out MI and other causes of cardiac disease. Cardiac Monitoring. Cardiac Echo. Consider cardiac MRI and cardiac biopsy. Initiate high dose methylprednisolone. If no improvement within 24 hours, add either infliximab, ATG or tacrolimus. Consult algorithm for more details. Resume therapy if there is a return to baseline and myocarditis is excluded or considered unlikely.
Grade ≥ 2 with confirmed myocarditis	Off protocol therapy. Admit to CCU (consider transfer to nearest Cardiac Transplant Unit). Treat as above. Consider high dose methylprednisolone. Add ATG or tacrolimus if no improvement. Off treatment.

* Including CHF, LV systolic dysfunction, Myocarditis, CPK, and troponin
** Patients with evidence of myositis without myocarditis may be treated according as "other event"
NOTE: The optimal treatment regimen for immune mediated myocarditis has not been established. Since this toxicity has caused patient deaths, an aggressive approach is recommended.

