7.1 Step 1: Therapeutic Parameters

Treatment should start within seven working days after registration (see Section 5)

	Screening ¹	Cycle 1 ^{1,2} (day 1)	Cycle 1 mid ² (day 15)	Cycle 2 ² (day 29)	Cycle 2 mid ² (day 43)	Cycle 3+ ² (day 57)	Post Treatment Follow Up ³
History and physical exam ⁵	X	X	X	X	X	X	X
Performance status, vital signs ⁵	X	X	X	X	X	X	
Complete blood count with differential ⁶	X		X	X	X	X	
Blood chemistry tests ⁷	X		X	X	X	X	
PT/INR and PTT	X						
Thyroid tests (TSH and reflex free T4) ⁴	X			X		X	
Electrocardiogram (ECG) ⁴	X			X		X	
Echocardiogram/MUGA ⁸	X						
Urine protein assessment ⁹	X			X		X	
Serum or Urine Pregnancy Test ¹⁰	X						
Toxicity Assessment		X	X	X	X	X	X
Tumor assessment imaging ^{11,16}	X					X ¹¹	X ³
Brain Imaging ¹²	X ¹²					X ¹²	
Nivolumab (Arms A, B, C, T)		X		X		X	
Cabozantinib (Arms B, C, T) ¹⁸		X	X	X	X	X	
Ipilimumab (Arm C)		X				X ¹⁵	
MANDATORY: Tumor Tissue ¹⁴	X						
Tobacco Use Assessment PROs ¹⁷							See Section 5.6

Cycle Length = 28 days

1. All baseline assessments must be done \leq 2 weeks before registration with the exception of imaging studies that must be done \leq 4 weeks before registration and brain imaging studies that must be done \leq 12 weeks before registration in patients without known brain metastases. Patients

with known brain metastases at baseline must have a brain MRI or head CT with contrast \leq 4 weeks prior to registration. All baseline laboratory tests can be used for Cycle 1 Day 1 treatment purposes.

2. Window for study visits and drug administration is \pm 3 days. Mid-cycle 1 and 2 visits are required for all arms. Starting with cycle 3, in-person visit by investigator is only required once per cycle.

NOTE: All hematology and chemistry assessments must be done \leq 72 hours prior to day 1 of the treatment cycle except for Cycle 1 Day 1 (see footnote 1).

3. Every 3 months until patient is 5 years from registration. Physical exam not required. If in person visit is not possible, patient should be contacted for follow up of vital status and assessment of any study-related toxicities until resolution. For patients that discontinued study therapy prior to radiographic progressive disease, tumor assessments should be performed at least every 3 months during long term follow up until progressive disease is documented.

- Rev. Add4

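### Section 5.4.10 names only ipilimumab as the drug to exclude before restart after grade 2 or 3 pneumonitis, although Arms A, B and T receive nivolumab without it (wording error, minor)

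*Combined protocol and SAP*

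**What the plan says.** The table in Section 5.4.10 sets the next dose of nivolumab with or without ipilimumab. At grades 2 and 3 the dose is held pending evaluation. Both rows then give one restart condition: "Resume no change in dose after pulmonary and/or ID consultation excludes ipilimumab and associated lymphocytic pneumonitis as the cause of the pneumonitis". Both rows also take the patient off study if steroids are needed. At grade 1 or lower, besides resolution to baseline, the condition names no drug: "Resume no change in dose after pulmonary and/or ID consultation excludes lymphocytic pneumonitis". Grade 4 ends protocol therapy.

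The same section recognises all three agents as possible causes: "Pneumonitis has been associated with cabozantinib, nivolumab, and ipilimumab therapies individually". It adds of pneumonitis: "In general it is difficult to definitively diagnose and can be life threatening".

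Sections 5.1.1 to 5.1.4 give nivolumab on every arm and ipilimumab on Arm C only ("Ipilimumab 1 mg/kg over 90 minutes every 8 weeks, ongoing"). The schedule in Section 7.1 agrees.

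**The concern.** A restart rule should name the drug being restarted, or name the event without naming a drug. These two rows do neither for nivolumab. A site on Arm A, B or T that followed the words literally could satisfy the condition at once, because a drug that was not given cannot be the cause, and could resume nivolumab without a finding on nivolumab.

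The condition matters because grade 3 pneumonitis can lead to restart at all. For immune-related liver and neurologic events grade 3 ends treatment, and for endocrine and other events it does so with stated exceptions. Under Section 5.4.2 the antibodies have no reduced dose level, so a restart is at full dose. Section 1.6 lists pneumonitis among the serious events seen with nivolumab, "with noted pulmonary toxicity resulting in 3 deaths".

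**Working it through.** No formula or stated figure is involved. The check sets the condition beside the regimens and the neighbouring rules.

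1. **Which drug is restarted, and which is named** (Sections 5.1.1 to 5.1.4, 5.4.10, 7.1):

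| Arm | Regimen | Antibody restarted | Named in grade 2–3 condition | Restarted but not named |
|---|---|---|---|---|
| A | nivolumab | nivolumab | ipilimumab (not given) | nivolumab |
| B | nivolumab + cabozantinib | nivolumab | ipilimumab (not given) | nivolumab |
| C | nivolumab + cabozantinib + ipilimumab | nivolumab and ipilimumab | ipilimumab | nivolumab |
| T | nivolumab + cabozantinib | nivolumab | ipilimumab (not given) | nivolumab |

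Nivolumab goes unnamed on all four arms. On three of them the named drug is not in the regimen.

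2. **Whether the omission could be intended.** Section 5.4.10 itself associates pneumonitis with nivolumab individually, and the nivolumab risk list in Section 5.3.2 includes it. The table in Section 5.4.3 rates pneumonitis as more common among immune-related toxicities and less common for cabozantinib. Nothing suggests that nivolumab was meant to be exempt.

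3. **How a comparable rule is worded.** For suspected myocarditis, Section 5.4.19 states the condition by event: "Resume therapy if there is a return to baseline and myocarditis is excluded or considered unlikely". That form works on every arm.

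4. **Whether other text supplies the missing condition.**
   - The note under the pneumonitis table treats inflammatory pneumonitis as a diagnosis of exclusion and names no drug. It expects most patients with hypoxia or respiratory failure to receive steroids, which at grade 2 or 3 takes them off study.
   - The pulmonary algorithm, to which the table refers, continues immunotherapy in its visible text only where the cause is non-inflammatory.
   - Section 5.4.26 says that patients for whom the investigator judges continued dosing a substantial clinical risk should go off protocol treatment.
   - Section 5.2.10 requires a 24-hour report of treatment-related grade 3 to 5 pneumonitis.
   - Section 5.4.3 says the management guidelines are not mandatory and leaves room for investigator discretion.

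   These limit the consequence. None of them states, for grades 2 and 3, that nivolumab must be excluded as the cause.

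5. **Whether anything statistical moves.** The early safety trigger in Section 9.8.2 (3 or more treatment-related grade 3 to 5 pneumonitis events among 15 patients) counts events whatever the restart row says. The PFS analysis and sample size are unaffected.

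**The case against.** The strongest reply is that no competent site would read the rows so literally. The column header says nivolumab with or without ipilimumab, so on Arms A, B and T the dose being held is plainly nivolumab. The section has just said that nivolumab can cause pneumonitis. The table's note and the algorithm text are drug-neutral and point to the right question: is this inflammatory or not? Drug naming is loose elsewhere too: the neurologic table in Section 5.4.12 is headed for nivolumab alone although Arm C also receives ipilimumab.

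Much of this stands. It makes the harmful reading unlikely and the affected group small. It does not make the two rows correct, because a clinician still has to infer what the restart rule should say.

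Stronger readings are tempting, and the documents do not support them:

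- *The protocol lets sites restart nivolumab without considering it as a cause.* The header, the note and the algorithm text point the other way.
- *Grades 2 and 3 have a weaker test than grade 1.* This holds only if the word associated is tied to ipilimumab alone. If it is not, the rows also require lymphocytic pneumonitis to be excluded, as grade 1 does.
- *The deaths noted in Section 1.6 give the size of the risk.* They come from another study and say nothing about patients restarted after grade 2 or 3 pneumonitis without steroids.
- *Most of the trial is exposed.* Arms A, B and T would hold 48 + 48 + 25 = 121 of 169 planned patients, about 72% (144 randomised 1:1:1, plus up to 25 on Arm T). That is the share enrolled where the wording does not fit, not the share harmed.

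**Conclusion.** The point holds as a minor wording error in a safety rule. On Arms A, B and T the literal grade 2 and 3 restart condition does not address the drug being restarted; on Arm C it omits one of the two antibodies.

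The practical effect is small and cannot be sized. The relevant group is patients with grade 2 or 3 pneumonitis who do not need steroids and are considered for restart, at a site that reads the row literally. The documents give no rate for this group, and it may be close to empty.

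The conclusion rests on the text that could be read. The algorithm flowchart and the note to the caret mark on the grade 2 row were not visible; either might already cover nivolumab. Their absence from the extracted text is not a fault in the plan.

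**What to change.** In both the grade 2 and grade 3 rows, replace the exclusion condition with: *excludes nivolumab- and/or ipilimumab-associated (immune-mediated, including lymphocytic) pneumonitis as the cause of the pneumonitis*. When editing, check that the flowchart and the caret note agree with it.

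The cost is a few words in two rows of one table at the next amendment. It adds no procedure or data collection and has no statistical consequence. The responses to the sponsor's review of Amendment 2 say the study was suspended for slow accrual and that further design changes had stopped. This is a correction, not a design change; the listed addendum made a similar one to the fatigue table in Section 5.4.14. If the trial stays closed, the benefit is mainly to any later protocol that reuses the table.
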